Clinical study protocol

Protocol Title: The efficacy and mechanisms of transcutaneous auricular vagus nerve stimulation on symptoms in patients with constipation-predominant irritable bowel syndrome

NCT NUMBER: NCT05392439

Document Date: 5/25/2022

Principal Investigator: [name]

Sponsor: Shanghai East Hospital, Tongji University

Title	The efficacy and mechanisms of transcutaneous auricular vagus nerve stimulation on symptoms in patients with constipation-predominant irritable bowel syndrome				
Protocol number	2020-006				
Sponsor	Shanghai Fast Hospital Tongii University				
Indication	Constinution-predominant Irritable Rowel Syndrome (IRS-C)				
Objective/Aim	This study aims to investigate the effects and possible mechanisms of				
	transcutaneous auricular vagal nerve stimulation (taVNS) on abdominal				
	pain and other symptoms in patients with IBS-C				
Sample size	N = 42				
Case selection	Inclusion criteria				
criteria	1) age $18-75$ years.				
	2) willing to sign a written informed consent form				
	3) met the Rome IV diagnostic criteria for IBS-C				
	Exclusion criteria:				
	1) had a history of previous abdominal surgery (other than appendectomy),				
	2) suffering from carcinoma,				
	3) had any organic diseases causing constipation or neurologic diseases				
	such as multiple sclerosis, rachischisis, Parkinson's disease or spinal cord				
	injury,				
	4) taking antidepressant agents including tricyclic antidepressants and				
	selective serotonin reuptake inhibitors,				
	5) had a serious concomitant disease of the heart, liver, kidney, or diabetes,				
	6) women during pregnancy or lactation,				
	7) participating in another trial or enrolled in a trial during the past month,				
	8) allergic to surface electrodes.				
Timeline	1) July 2019 - August 2019: Screen and confirm the clinical diagnosis of				
	IBS-C patients, and estimate the sample content				
	2) September 2019–July 2020: Patient recruitment, and for the selected				
	participants, signed an informed consent form, underwent percutaneous				
	auricular vagus nerve stimulation treatment, and collected outcome				
	measures				
	3) August 2020-October 2020: Data analysis				
Statistical analysis	The independent sample t-test is used to assess the difference between the				
	sham-taVNS and taVNS groups; The paired student's t-test is applied to				
	evaluate the differences before and after the taVNS or sham-taVNS				
	treatment. $P < 0.05$ is considered statistically significant.				

Clinical study summary

Background

Irritable bowel syndrome (IBS) is a clinical syndrome characterized by persistent or intermittent attacks, abdominal pain, abdominal distension, defecation habits and (or) changes in stool characteristics. According to the world-wide population survey, the global prevalence of IBS is about 11.2% (95% CI: 9.8-12.8) (1), and the prevalence of IBS in China is about 5-10% (2). According to Rome IV diagnostic criteria (3), IBS can be divided into four types: constipation type (IBS-C), diarrhea type (IBS-D), mixed type (IBS-M) and unclassified type (IBS-U). Among them, IBS-C accounted for about 27% of the total prevalence (4). The persistent or intermittent symptoms of patients bring a lot of inconvenience and pain, resulting in a significant decline in the quality of life, but also increased the burden of the social health system.

The etiology and pathogenesis of IBS have not been fully elucidated, but many factors are involved, including genetic factors, intestinal infection, mucosal immune and inflammatory response, altered gastrointestinal motility, visceral hypersensitivity, post infectious reactivity, brain-gut interactions, disturbance of intestinal flora, food sensitivity or stress(5-8), among which altered gastrointestinal motility and visceral hypersensitivity have been considered to be the main pathophysiological basis. At present, various drugs are used for pharmacologic treatment. Laxatives and prokinetics are used for constipation, while antispasmodics and antidepressants are prescribed for abdominal pain, which in turn may impair gastrointestinal motility and thus could worsen constipation (9, 10). Additionally, such medications can only relieve symptoms temporarily, and long-term medication is expensive and easy to relapse after withdrawal (11). Accordingly, patients often seek complementary and alternative therapies (12).

It is well known that the autonomic nervous system is a complex hierarchically controlled system, providing a neural link between the brain and the body that integrates the external environment with the internal milieu to maintain homeostasis. It is composed of two broadly opposing branches, the sympathetic and parasympathetic nervous system, and the vagus nerve is the main neural substrate of the parasympathetic nervous system (13). A relative paucity of vagal activity, has been implicated in the pathophysiology of a number of disorders including, but not limited to, functional dyspepsia, irritable bowel syndrome (IBS), inflammatory bowel disease, and chronic pain syndrome (14, 15). Thus, vagus nerve stimulation is of interest as a potential therapeutic intervention.

Vagus nerve stimulation (VNS), approved by FDA for epilepsy and drug-resistant depression (16), has been extended in recent years as a complementary and alternative treatment to treat other diseases, including gastrointestinal dysmotility, inflammation and pain (17-19). The classic implantable device consists of an electrode, which is wrapped around the left vagus nerve, and an implantable unit, positioned below the collarbone and containing the battery and pulse generator. However, despite being a minimally invasive procedure, the involvement of surgery, perioperative risks, and potentially significant side effects have limited its applicability.

Transcutaneous vagus nerve stimulation (tVNS) is a noninvasive method that has been developed to overcome these limitations. The rationale for using tVNS on the ear is based on anatomical studies that suggest that the ear is the only place on the surface of the human body where there is afferent vagus nerve distribution (20, 21). Thus, direct stimulation of the afferent nerve fibers on the ear should produce an effect similar to classic VNS. In recent years, transcutaneous auricular vagus nerve stimulation (taVNS)

has been reported to improve gastrointestinal disorders, including abdominal pain (22), constipation (23) and functional dyspepsia (24), but there is no study on ta VNS in the treatment of IBS-C. Based on the integrative effects of taVNS on both pain and motility we observed in the animal model of functional dyspepsia and patients with abdominal pain-related functional gastrointestinal disorders (22, 24, 25), we hypothesized that taVNS might improve symptoms in patient with IBS-C by enhancing vagal efferent activity. The aim of this study is to investigate the effects and mechanisms of taVNS on symptoms in patients with IBS-C.

Methods

Study design and plan

(1) The patients diagnosed with IBS-C are screened and the sample size is estimated;

(2) The inclusion and exclusion criteria are selected and informed consent is signed;

(3) The treatment group is treated with taVNS, while the control group is treated with sham taVNS. The blood samples are collected and outcome measures are taken;

(4) Samples are sent for inspection and the results are statistically analyzed.

Patients

Inclusion criteria:

1) age 18–75 years,

2) willing to sign a written informed consent form,

3) met the Rome IV diagnostic criteria (26) for IBS-C.

Exclusion criteria:

1) had a history of previous abdominal surgery (other than appendectomy),

2) suffering from carcinoma,

3) had any organic diseases causing constipation or neurologic diseases such as multiple sclerosis, rachischisis, Parkinson's disease or spinal cord injury,

4) taking antidepressant agents including tricyclic antidepressants and selective serotonin reuptake inhibitors,

5) had a serious concomitant disease of the heart, liver, kidney, or diabetes,

6) women during pregnancy or lactation,

7) participating in another trial or enrolled in a trial during the past month,

8) allergic to surface electrodes.

Withdrawal criteria:

1) The subject or his legal guardian voluntarily requests to withdraw;

- 2) Violation of inclusion / exclusion criteria;
- 3) Withdraw when other unexplained serious complications occur;
- 4) If pregnancy occurs during treatment, withdraw from the study;

5) For safety reasons, the study sponsor proposed to stop the study;

6) Subjects whose ethics committee decided to stop the study;

7) Subjects who are considered unsuitable for further study.

The reason and date of withdrawal are recorded, and the withdrawal rate is counted at the end of the study.

The subjects who withdraw from the study will take appropriate treatment measures according to the judgment of the researchers.

Trial interventions

Enrolled patients will be randomized to undergo either taVNS or sham-taVNS. The taVNS treatment is performed at auricular cymba concha, while Sham-taVNS is performed at a sham point (elbow area). **Study Design and Protocol**

Enrolled patients are randomly divided into two groups (taVNS and sham-taVNS) with a ratio of 1:1 according to a computer-generated random digital table. The sample size is calculated by G*power analyses based on our preliminary study. One week before the start of the study, patients are asked to stop all constipation and IBS medications, including laxatives, prokinetic agents, probiotics, and antispasmodics. After one-week run-in period, patients in each group are requested to complete the following questionnaires once a week: the visual analog scale (VAS) for abdominal pain, IBS symptom severity score (IBS-SSS) for the overall IBS symptoms, IBS quality of life questionnaire (IBS-QOL) for patient's quality of life, Bristol Stool Form Scale (BSFS) for the stool type, Self-Rating Anxiety Scale (SAS) for anxiety, Self-Rating Depression Scale (SDS) for depression, and the bowel diary for the number of complete spontaneous bowel movements per week. Autonomic function is assessed at the baseline and after 4 weeks of treatment. by the spectral parameters of heart rate variability (HRV), calculated using spectral analysis of R-R intervals in electrocardiogram (ECG). A blood sample is taken at 8 a.m. at baseline and after 4 weeks treatment, Serum and plasma are separated and frozen at - 80 °C. The chronic taVNS and sham-taVNS intervention is performed twice a day (8am and 8pm) for half an hour each time, lasting for four weeks. During the run-in and treatment periods, only Macrogol 4000 and pinaverium are permitted for use, when the patient could not tolerate symptoms of constipation and abdominal pain. The flowchart is shown in Figure 1, and the study schedule is detailed in Table 1.

Figure 1. Flowchart of the study design.

	Baseline	Week 1	Week 2	Week 3	Week 4
Consent	×				
VAS	×	×	×	×	×
IBS-SSS, IBS-QOL	×	×	×	×	×
SAS, SDS, BSFS	×	×	×	×	×
HRV	×				×
Blood	×				×

Table 1. Study schedule. A bowel diary is recorded during the treatment.

VAS, visual analog scale; IBS-SSS, IBS symptom severity score; IBS-QOL, IBS quality of life questionnaire; SAS, Self-rating Anxiety Scale; SDS, Self-rating Depression Scale; BSFS, Bristol stool form scale; HRV, heart rate variability.

Randomization

Enrolled patients are randomly divided into two groups (taVNS and sham-taVNS) with a ratio of 1:1 according to a computer-generated random digital table, which contains 21 odd numbers and 21 even numbers. Odd numbers represent taVNS, while even numbers represent sham-taVNS, and enter corresponding groups according to the sequence of patients.

Blinding

The patients are blinded to the type of treatment.

Serious adverse events (SAEs)

Pain at the stimulation site and allergy to the electrode are adverse events. Lowering the intensity of stimulation can relieve or eliminate pain. If the patient is allergic to the electrode, we will terminate the treatment and let the patient withdraw from the study.

Statistics

Quantitative variables are reported as means \pm standard deviations (SD), while categorical data qualitative variables are presented as absolute values and percentages. Categorical data are compared using the chi-squared test. The independent sample t-test is used to assess the difference between the sham-taVNS and taVNS groups; The paired student's t-test is applied to evaluate the differences before and after the taVNS or sham-taVNS treatment. *P*<0.05 is considered statistically significant.

Sample size estimation

G-Power software is used for calculation, and the steps are as follows:

- 1. T test, mean difference between two dependent means (two groups)
- 2. A priori: compute required sample size, given α , power, and effect size
- 3. Tails: One
- 4. Effect size: In the previous study, the number of spontaneous defecation was: 2.3 ± 2.1 (SD) in sham stimulation group; 3.7 ± 1.4 (SD) in true stimulation group. Therefore, the effect size dz=0.784.
- 5. $\alpha = 0.05$; $\beta = 0.2$, $1 \beta = 0.8$;

Based on the above data, G-Power software calculated total sample size: n = 42

Ethics committee review

The protocol, written informed consent, and information directly related to the subjects will be submitted to the Ethics Committee for written approval before the study can be formally carried out. The researcher must submit an annual report of the study to the ethics committee at least annually (if applicable). When the study is terminated and / or completed, the researcher must inform the ethics committee in writing; the researcher must timely report to the ethics committee all changes in the research work (such as the revision of protocol and / or informed consent number), and shall not implement these changes without the approval of the ethics committee, unless it is made to eliminate obvious and direct risks to the subjects Changes to the contract. When this happens, the ethics committee will be informed.

Informed consent

The researcher must provide the subject or his legal representative with the informed consent which is easy to understand and approved by the ethics committee, and give the subject or his legal representative sufficient time to consider the study. The subject shall not be enrolled until the written informed consent is obtained from the subject. All updated versions of informed consent and written information will be provided to the subjects during their participation. Informed consent should be kept as an important document of clinical trials for future reference.

Confidentiality measures

Subject's medical records (research medical records, examination reports, etc.) will be kept in the hospital, and the doctor will record the examination results in outpatient medical records. Researchers, sponsor representatives and ethics committee will be allowed to access subject's medical records. Any public report on the results of this study will not disclose subject's personal identity. We will make every effort to protect the privacy of subject's personal medical data within the scope permitted by law. Subject's medical records will not be used for any purposes other than this study.

Timeline

1) July 2019 - August 2019: Screen and confirm the clinical diagnosis of IBS-C patients, and estimate the sample content

2) September 2019–July 2020: Patient recruitment, and for the selected participants, signed an informed consent form, underwent percutaneous auricular vagus nerve stimulation treatment, and collected the outcome measures

3) August 2020-October 2020: Data analysis

References

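### The available text schedules no bowel diary week before treatment, so the before/after t-test has no recorded baseline for weekly complete spontaneous bowel movements

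*Combined protocol and SAP*

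**What the plan says.** Study Design and Protocol lists seven instruments under one timing rule: "After one-week run-in period, patients in each group are requested to complete the following questionnaires once a week". The last of them is "the bowel diary for the number of complete spontaneous bowel movements per week".

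Table 1 has columns for Baseline and Weeks 1 to 4. VAS, IBS-SSS, IBS-QOL, SAS, SDS, BSFS, HRV and blood are all marked at Baseline, and so is consent. The diary has no row. It appears only in the caption: "Table 1. Study schedule. A bowel diary is recorded during the treatment".

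The run-in week is described as a medication stop: "One week before the start of the study, patients are asked to stop all constipation and IBS medications". A rescue rule covers it as well: "During the run-in and treatment periods, only Macrogol 4000 and pinaverium are permitted for use". No diary task is given for that week.

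The Statistics section compares the arms with an independent-samples t-test. For change within an arm, a paired "t-test is applied to evaluate the differences before and after the taVNS or sham-taVNS treatment". Neither sentence names an outcome, and no baseline adjustment is planned.

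**The concern.** Most instruments in the list can be completed at a single visit. A count per week cannot: someone has to record a week. If recording starts with stimulation, the earliest available count is already an on-treatment value. A before/after test on this outcome would then have to use treatment week 1 or the patient's recall as its starting point, and neither is a prospective pre-treatment measurement. If treatment acts within the first week, using week 1 would also understate the change.

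Bowel frequency is a core symptom in IBS-C, and the trial was sized on a related count ("In the previous study, the number of spontaneous defecation was" is how the effect-size step begins). Without a pre-treatment week, the report could not show whether the arms started level on it, and the count could not be used as a covariate. A prospective diary week cannot be recovered afterwards.

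**Working it through.** **1. The schedule, set side by side**

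| Measure | Baseline mark in Table 1 | Baseline named in the text |
|---|---|---|
| VAS, IBS-SSS, IBS-QOL, SAS, SDS, BSFS | yes | no; the rule is weekly, after the run-in |
| HRV, blood | yes | yes (for HRV: "Autonomic function is assessed at the baseline and after 4 weeks of treatment") |
| Bowel diary count | no row | no; the caption names the treatment period |

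Eight measures have a baseline mark and the diary has none. The rescue-medication sentence treats run-in and treatment as two periods. In the protocol's own terms, a diary placed in the treatment period is therefore not thereby placed in the run-in.

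**2. The plan's own figure**

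Inputs from Sample size estimation: 2.3 (SD 2.1) under sham, 3.7 (SD 1.4) under true stimulation, one tail, α = 0.05, power 0.8. From Randomization: 21 per arm.

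- Pooled SD = √((2.1² + 1.4²)/2) = √3.185 = 1.785.
- d = (3.7 − 2.3)/1.785 = 0.784, as stated.
- Two independent means, 21 per arm, one-sided 0.05: noncentrality = 0.784 × √(21/2) = 2.54, df = 40, power 0.803.

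N = 42 reproduces as a one-sided comparison of two independent groups. That calculation uses no baseline count, so the diary gap does not touch it. (The section labels the test as one of dependent means; that is a separate matter.)

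**3. How far apart the arms could start by chance**

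Assumption: the sizing SDs, which are for spontaneous defecation in a previous study, stand in for the SD of the diary count.

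- SE of a baseline difference = 1.785 × √(2/21) = 0.551 per week.
- 95% range = ±1.96 × 0.551 = ±1.08 per week (±0.85 at SD 1.4, ±1.27 at SD 2.1).

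This is chance imbalance and not bias, and the standard error of the unadjusted t-test already allows for it. With equal SDs at baseline and outcome, it carries into the outcome in proportion to the correlation r: r × 1.08 = ±0.32, ±0.54 or ±0.76 per week at r = 0.3, 0.5 or 0.7. The documents do not give r.

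**4. What a baseline count could add**

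With the baseline count as a covariate, the residual SD shrinks by √(1 − r²). The effective d is 0.784/√(1 − r²), with df = 39.

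| Assumed r | Effective d | One-sided power, N = 42 |
|---|---|---|
| not adjusted | 0.784 | 0.803 |
| 0.3 | 0.822 | 0.835 |
| 0.5 | 0.905 | 0.892 |
| 0.7 | 1.098 | 0.968 |

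Power is computed from the unrounded d. The Statistics section does not state sidedness; two-sided at 0.05, the corresponding values are about 0.70, 0.74, 0.82 and 0.93. These gains need both the diary week and an adjusted analysis, and the plan contains neither.

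**The case against.** The strongest defence is the shared list. The diary sits under the same timing rule as six instruments that do have a Baseline mark, so in this protocol that rule evidently includes a baseline assessment. A caption note is an ordinary way to show a continuous record that does not fit a visit grid, and this one does not say that the diary is kept only then. The text also refers to Figure 1 for the study flow; that figure is not available and may show a run-in diary.

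This defence stands in part. It makes an intended baseline plausible, and it means the gap is unconfirmed. It does not supply a recorded week: a per-week count first requested after the run-in is recall unless the diary was issued a week earlier, and the available text does not say that it was.

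It is also fair to say that the stakes are narrow. The paired test names no outcome, and this count is nowhere named as primary. A within-arm change after stopping laxatives would be weak evidence of efficacy in any case.

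A reader might infer that the main comparison or the sample size is undermined. The documents do not support that: the randomised t-test needs only on-treatment counts, and so does N = 42. Nor do they support reading the power figures as a loss in the current plan, because no baseline adjustment is planned.

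**Conclusion.** The point holds as a low-severity, cheap improvement. On the available text, a stated type of analysis (the paired before/after test) has no prospectively recorded starting week for one outcome, and baseline balance on that outcome cannot be checked. The eight measures marked at Baseline keep their starting values.

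That no pre-treatment diary exists is a stronger reading that the text does not establish, given the unseen figure and the shared list. The ±1.08 per week describes how far the arms could differ at the start by chance; it is not an estimate of error in the treatment effect. The possible precision gain runs from small (0.803 to 0.835) to substantial (0.968). It rests on assumed correlations and on SDs borrowed from a related count in a previous study.

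**What to change.** - Obtain consent before the run-in. Table 1 marks it at Baseline, which is too late for a run-in diary.
- Issue the diary on day 1 of the existing run-in week.
- Add a Run-in column and a bowel diary row to Table 1, and extend the caption to cover the run-in as well as the treatment.
- Define the run-in week count as the baseline for complete spontaneous bowel movements per week.
- To gain precision, also compare the arms on this count by ANCOVA with the baseline count as covariate. Adding the diary alone does not deliver the power figures above.

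**Cost:** earlier consent and seven extra diary days per patient (42 × 7 = 294 patient-days). The trial is no longer, because the run-in already exists. The baseline week may partly reflect medication withdrawal. Under randomisation that is expected to be equal in both arms, but it is a reason not to read a within-arm change as efficacy.

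If Figure 1 already schedules a run-in diary, only Table 1 and its caption need aligning. The Timeline ends in October 2020 and the document is dated May 2022, so the data may already be in hand. In that case, state whether a run-in diary was kept; if it was not, make no before/after claim for this count.

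### The plan has no general adverse-event definition and schedules no adverse-event enquiry, so events that do not cause withdrawal have no stated route into the data

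*Combined protocol and SAP*

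**What the plan says.** The Serious adverse events (SAEs) section of the combined protocol and SAP opens with "Pain at the stimulation site and allergy to the electrode are adverse events". Its other two sentences deal with handling: "Lowering the intensity of stimulation can relieve or eliminate pain" and "If the patient is allergic to the electrode, we will terminate the treatment and let the patient withdraw from the study". The section does not define an adverse event in general, does not say what makes an event serious, and describes no recording, grading or causality assessment.

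Table 1 has rows for consent, VAS, IBS-SSS and IBS-QOL, SAS, SDS and BSFS, HRV, and blood. Its caption adds the diary: "Table 1. Study schedule. A bowel diary is recorded during the treatment". There is no adverse-event row.

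Harms also appear in the Withdrawal criteria, which include "Withdraw when other unexplained serious complications occur", pregnancy during treatment, and a sponsor decision to stop on safety grounds. That section ends with "The reason and date of withdrawal are recorded, and the withdrawal rate is counted at the end of the study".

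The Statistics section describes tests for quantitative and categorical data but mentions no safety data. The Blinding section refers to patients and to nobody else. The stated aim is "The aim of this study is to investigate the effects and mechanisms of taVNS on symptoms in patients with IBS-C"; no safety objective or endpoint is given.

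**The concern.** The treatment is intended to raise vagal efferent activity, and the Background says that no earlier study has used it in IBS-C. Systemic effects are therefore plausible on the plan's own rationale, yet the only reactions that it names are local to the electrode. If nobody is required to ask about anything else, a patient who feels unwell but continues may leave no trace in the data, and the analyst cannot recover that information afterwards.

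Two later statements are at stake. One is any comparison of harms between taVNS and sham. The other is a conclusion that taVNS is safe or well tolerated in this population: a count of zero would not distinguish the absence of events from the absence of a question.

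**Working it through.** The plan gives no figure on this point to reproduce. The check is to trace, for each kind of event, whether the text provides a way into the data.

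**Inputs.** Serious adverse events (SAEs), Withdrawal criteria, Study Design and Protocol with Table 1, Blinding, and Statistics.

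**Step 1: exposure.** The plan states "The chronic taVNS and sham-taVNS intervention is performed twice a day (8am and 8pm) for half an hour each time", for four weeks. That is 2 × 7 × 4 = 56 sessions, or 56 × 0.5 = 28 hours of stimulation per patient.

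**Step 2: route into the data, by kind of event.**

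| Kind of event | Route stated in the plan |
|---|---|
| Electrode allergy | Yes: the patient is withdrawn, and reason and date are recorded |
| Serious complication leading to withdrawal | Yes: reason and date of withdrawal |
| Pregnancy | Yes: it is a withdrawal criterion |
| Worsening abdominal pain, bowel or overall IBS symptoms | Yes, as scores: VAS, IBS-SSS and BSFS at baseline and Weeks 1 to 4, plus the bowel diary during treatment |
| Worsening anxiety or depression | Yes, as scores: SAS and SDS at the same times |
| Stimulation-site pain that does not cause withdrawal | Named as an adverse event; handling stated, recording not stated |
| Any other event in a patient who continues (for illustration, dizziness or palpitations) | None stated |

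The last row is the gap. The row above it is a lesser one: the event is named, but no form, visit or grade is attached to it.

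**Step 3: could other assessments fill the last row?** HRV and blood are taken at baseline and Week 4 only. HRV is described as a measure of autonomic function, and the blood is separated and frozen. Neither is described as safety monitoring, and neither asks the patient about new events. The weekly questionnaires cover pain, bowel function, quality of life, anxiety and depression. None is described as an open enquiry.

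**Step 4: effect on a comparison between arms.** Let p be the true event rate in an arm and c the probability that an event is captured. The expected observed rate is p × c, so the observed ratio of taVNS to sham is (p_taVNS / p_sham) × (c_taVNS / c_sham). The second factor is 1 only if capture is the same in both arms. Without a scheduled question, c depends on what patients volunteer and what staff choose to note. Active stimulation is at the ear and sham at the elbow, so anyone who sees the electrode in place knows the arm, and the plan does not say that staff or assessors are blinded. Nothing in the plan holds c_taVNS and c_sham equal, and neither can be estimated from the data that it collects.

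**The case against.** The strongest reply is that the plan is not blind to harms. The Withdrawal criteria foresee serious complications beyond the two named reactions, and the reason and date of each withdrawal are kept. Withdrawals by reason could therefore be tabulated by arm, and the chi-squared test already listed could be applied to them. The trial also claims no safety objective, so it promises no safety conclusion.

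Much of this stands, and it rules out three stronger readings that a reader might infer:

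- **That the plan closes the list of adverse events at two.** The sentence says that these two are adverse events. It does not say that they are the only ones, and the Withdrawal criteria point the other way. It can be read as a list of expected device reactions, so the fault is silence about everything else.
- **That all systemic harms would go unrecorded, or that no safety statement could be made.** Complications and pregnancies that end participation are recorded, and withdrawals by reason can be reported.
- **That deterioration after stopping IBS medication would be missed.** Pain, overall IBS symptoms, stool form, anxiety and depression are scored weekly in both arms during treatment, and bowel movements are kept in the diary.

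What the reply does not answer is the event that does not end participation. The withdrawal route cannot reach it, and the word serious in that route is undefined. The absence of a safety objective limits what the report may claim; it does not remove participants' interest in having harms noticed.

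There is also a practical objection. The document is dated 5/25/2022, while its Timeline places recruitment and treatment between September 2019 and July 2020. If that timeline was kept, a new row in Table 1 comes too late. The documents do not show whether it was.

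**Conclusion.** The point holds as an omission. There is no general definition of an adverse or serious adverse event and no scheduled enquiry, so events outside the weekly scores that do not cause withdrawal may be missed in either arm. Any between-arm comparison of harms, or conclusion that taVNS is safe, would be unsupported. A statement confined to withdrawals and their reasons would be supported.

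The size cannot be put as a number, because the documents give no event rates and no capture rates. A reader might take the exact one-sided 95% upper limit for zero events in 21 patients, 1 − 0.05^(1/21) = 0.133, as the measure of the flaw. It is not. It is a property of an arm of 21 and would apply just as much with full collection. Without systematic enquiry even that limit could not be claimed.

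The conclusion assumes that the flowchart in Figure 1, which could not be read here, adds no adverse-event enquiry, and that no separate case report form supplies one. Dizziness and palpitations are illustrations; the documents do not mention them.

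**What to change.** - Add an adverse-event row to Table 1 at Weeks 1 to 4: one open question, worded and asked identically in both arms, at the existing weekly questionnaire.
- For each event record date, severity, seriousness and relation to stimulation. Keep stimulation-site pain and electrode allergy as expected events, recorded in the same way.
- Put a standard definition of a serious event under the SAE heading.
- Add to Statistics a descriptive table of events by arm.

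The cost is one question a week and one table. No visit is added, and neither the sample size nor the efficacy analysis changes. The downside is small: more non-specific events to record. How events are handled clinically is left to the protocol.

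If collection has already finished, the question cannot be asked retrospectively to the same standard. The report should then say that adverse events were not systematically sought, and confine itself to withdrawals by reason and arm.
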